## **2.8 Safety analyses**

For all safety analyses, the Safety set will be used. The summary tables by visit will include the assessments at the scheduled visits unless otherwise specified. All listings will include unscheduled visits.

At the interim analyses, as described in [Section 2.1](#), all available data at the cut-off date will be included for safety analyses.

For the Week 28 IA, AEs will be summarized up to Week 28 and entire treatment period. Exposure adjusted event rate will be provided for entire treatment period. For laboratory, ECG and vital signs, by-visit summaries will be provided up to Week 28. Incidence rates of notable abnormalities will be provided for the period up to Week 28 and entire treatment period.

For the Week 48 IA, AEs will be summarized up to Week 48 and entire treatment period. Exposure adjusted event rate will be provided for entire treatment period. For laboratory, ECG and vital signs, by-visit summaries will be provided up to Week 48. Incidence rates of notable abnormalities will be provided for the period up to Week 48 and entire treatment period.

For the final analysis, all safety data will be summarized for entire treatment period.

### **2.8.1 Adverse events (AEs)**

AEs will be coded using the MedDRA dictionary that provides the primary system organ class (SOC) and preferred term (PT) information.

All information obtained on AEs will be displayed by participant. A listing will include all AEs collected on eCRF during the study from screening period and treatment period.

Treatment emergent AEs (events started after the first dose of study medication or events present prior to start of study treatment but increased in severity based on preferred term) will be summarized by presenting, the number and percentage of participants having any AE, having any AE in each primary SOC, and having each individual AE based on the PT. A participant with multiple AEs within a primary SOC is only counted once towards the total of the primary SOC.

The following summary tables will be provided.

- All treatment emergent AEs regardless of study drug relationship by SOC and PT
- All treatment emergent AEs regardless of study drug relationship by maximum severity, SOC and PT
- All treatment emergent AEs regardless of study drug relationship, leading to study drug discontinuation, by SOC and PT
- All treatment emergent AEs regardless of study drug relationship, requiring concomitant medication or non-drug therapy, by SOC and PT
- Treatment emergent serious AEs regardless of study drug relationship by SOC and PT
- Treatment emergent AEs related to study drug treatment by SOC and PT
- Treatment emergent serious AEs related to study drug treatment by SOC and PT
- A summary of death, serious AEs, AEs related to study drug treatment, AEs leading to study drug discontinuation

Exposure adjusted event rate (per 100 participant-years) of treatment emergent AEs will be summarized by SOC and PT. The event rate (ER) per 100 participant-years will be calculated as follows:

$$ER = 100 * \text{total number of occurrence of events} / \text{total participant-years},$$

where total participant-years is the sum of all participants' exposure times, i.e. duration of exposure from the day of the first dose of study treatment to the day of the last study visit.

To support the registration dossier, treatment emergent AEs will also be summarized by SOC, PT and onset period at the 28 Week IA and the 48 week IA using the data up to Week 28 and Week 48, respectively. Deaths, SAEs other than deaths, and AEs causing study treatment discontinuation will also be summarized. The following intervals will be used:

- 0-<4 weeks (1-<28 days)
- $\geq 4$ -<12 weeks ( $\geq 28$ -<84 days)
- $\geq 12$ -<24 weeks ( $\geq 84$ -<168 days)
- $\geq 24$ -<36 weeks ( $\geq 168$ -<252 days)
- $\geq 36$ -<48 weeks ( $\geq 252$ -<336 days)
- $\geq 48$  weeks ( $\geq 336$  days).

Note: at the Week 28 IA, the intervals after 24 weeks will be combined, i.e.,  $\geq 24$  weeks ( $\geq 168$  days).

Treatment emergent AEs will be summarized by SOC and PT and by the subgroups described in [Section 2.2.1](#) at the 28 Week IA and the 48 Week IA using the all available data at the time point for the analysis.

Serious adverse events, adverse events leading to study drug discontinuation, adverse events requiring interruption, and adverse events requiring concomitant medication or non-drug therapy will be listed if any.

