## **2 Statistical methods**

### **2.1 Data analysis general information**

The statistical analysis will be performed by Novartis using SAS 9.4 TS Level 1M6 or above.

Summary statistics for continuous variables will generally include n, mean, standard deviation, median, minimum, and maximum. For categorical variables, this will generally include frequency and percentage. For selected parameters, 25th and 75th percentiles will also be presented when applicable.

The data cut-off date for Week 28/Week 48 IA will be the date of Week 28/Week 48 visit for the last participant. For efficacy analyses, the data up to Week 28/Week 48 visit for each individual participant will be included. For safety analyses and summaries for treatments, all available data will be included.

No center-specific or stratified analyses will be performed.

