## **2.4 Treatments (study treatment, rescue medication, concomitant therapies, compliance)**

### **2.4.1 Study treatment / compliance**

The exposure to study drug (number of injections), duration of exposure (days) and total exposure in patient years will be summarized and listed for the Safety set. The number and percentage of participants of certain durations (any exposure, ≥4 weeks (28 days), ≥12 weeks (84 days), ≥24 weeks (168 days), ≥36 weeks (252 days), ≥48 weeks (336 days), etc.) will be provided.

For the interim analyses, the duration of exposure (days) for the continuation participants will be calculated as:

Duration of exposure (days) = the day of cut-off – the day of first dose of study treatment + 1.

For the interim analyses, the duration of exposure (days) for the discontinuation participants will be calculated as:

Duration of exposure (days) = the day of the last study visit – the day of first dose of study treatment + 1.

For the final analysis, the duration of exposure (days) will be calculated as:

Duration of exposure (days) = the day of the last study visit – the day of first dose of study treatment + 1.

The total exposure in patient years will be calculated as the total patient days divided by 365.25.

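### At the two interim analyses, SAP 2.4.1 ends exposure for continuing participants at the cut-off, but SAP 2.8.1 ends the event-rate denominator at the last study visit for everyone

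*SAP*

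**What the plan says.** SAP 2.4.1 (Study treatment / compliance) gives three rules for duration of exposure.

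- Interim, continuing: "For the interim analyses, the duration of exposure (days) for the continuation participants will be calculated as" follows: "Duration of exposure (days) = the day of cut-off", minus the first-dose day, plus 1.
- Interim, discontinued: "Duration of exposure (days) = the day of the last study visit", minus the first-dose day, plus 1.
- Final analysis, everyone: the same last-visit formula.

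The section then defines total exposure in patient-years as total patient days divided by 365.25.

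SAP 2.8.1 (Adverse events) defines the rate per 100 participant-years. It states that "total participant-years is the sum of all participants' exposure times", and explains those times as "duration of exposure from the day of the first dose of study treatment to the day of the last study visit". It has no separate rule for interim analyses and no reference to 2.4.1.

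SAP 2.8 makes the rate an interim output. For each of the Week 28 and Week 48 analyses it says: "Exposure adjusted event rate will be provided for entire treatment period". It also says that, at the interim analyses, "all available data at the cut-off date will be included for safety analyses".

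SAP 2.1 fixes the cut-off: "The data cut-off date for Week 28/Week 48 IA will be the date of Week 28/Week 48 visit for the last participant". SAP Section 4 lists no change that would reconcile the two definitions.

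**The concern.** One term, duration of exposure, has two end points for the same people at the same analysis. The cut-off is set by the last participant's visit, and injection visits are four weeks apart (Protocol 6.3.2 and Table 8-1). Most other continuing participants will therefore be between visits on that day, so their last study visit falls before the cut-off.

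Two things follow if each section is programmed as written. First, the interim report would carry one patient-year total in the exposure table and a smaller one under the event rates. Second, the numerator window would run to the cut-off while the denominator stopped earlier. Any event dated in the gap would be counted without the person-time in which it arose.

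SAP 2.14 says that the interim analyses support and supplement the registration dossier. Two unreconciled totals there would invite an avoidable query.

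**Working it through.** The documents state no person-time or event-rate figure, so there is nothing to reproduce. The check compares the two rules and then sizes the difference.

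**Step 1. The rules side by side**

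| Case | SAP 2.4.1 ends at | SAP 2.8.1 ends at | Agree? |
|---|---|---|---|
| Interim, continuing | cut-off | last study visit | no |
| Interim, discontinued | last study visit | last study visit | yes |
| Final analysis, all | last study visit | last study visit | yes |

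Within the first row, the participant whose Week 28 or Week 48 visit sets the cut-off has a gap of zero.

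**Step 2. Inputs**

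- From the documents: 14 participants (SAP 2.5.6); Week 28 = Day 197 and Week 48 = Day 337 (SAP Table 2-1); visits every 28 days, so on schedule the gap is 0 to 27 days, averaging 13.5; 365.25 days per year (SAP 2.4.1).
- Assumed: exposure of the other 13 participants, the actual gaps, the number of discontinuations, and 40 events for illustration.

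**Step 3. Formula**

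If all events up to the cut-off are captured, the literal 2.8.1 rate divided by the rate using 2.4.1 exposure is

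ratio = (sum of days to cut-off) / (sum of days to last visit).

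**Step 4. Illustration at Week 28**

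Take 14 continuing participants, one at 197 days with no gap and 13 at 365 days with an average gap of 13.5 days.

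- To cut-off: 197 + 13 × 365 = 4942 days = 13.53 patient-years.
- To last visit: 4942 − 13 × 13.5 = 4766.5 days = 13.05 patient-years.
- Ratio: 4942 / 4766.5 = 1.037.
- For 40 events: 295.6 against 306.5 per 100 patient-years.

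**Step 5. Other exposure lengths, same average gap, no discontinuations**

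| Analysis | Others' days to cut-off | Ratio |
|---|---|---|
| Week 28 | 365 | 1.037 |
| Week 28 | 533 | 7126 / 6950.5 = 1.025 |
| Week 48 | 505 | 6902 / 6726.5 = 1.026 |
| Week 48 | 673 | 9086 / 8910.5 = 1.020 |

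**Step 6. Varying the gap and discontinuations**

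Here the common gap runs from 7 to 27 days. Discontinued participants are given half the visit day as exposure and no gap.

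| Analysis (others' exposure) | None discontinued | 4 discontinued |
|---|---|---|
| Week 28 (365 days) | 1.019 to 1.077 | 1.017 to 1.067 |
| Week 48 (505 days) | 1.013 to 1.054 | 1.012 to 1.046 |

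**Step 7. Stress cases**

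Suppose every one of the other 13 is 27 days past the Week 28 or Week 48 visit.

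- Week 28: (197 + 13 × 224) / (14 × 197) = 3109 / 2758 = 1.127.
- Week 48: (337 + 13 × 364) / (14 × 337) = 5069 / 4718 = 1.074.

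These are the largest values with on-schedule visits and all 14 participants continuing. Missed or late visits would change them.

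**The case against.** **The clause may be shorthand.** The wording in 2.8.1 matches 2.4.1 in two of the three cases and may be a loose restatement that left out the interim continuing case. Two totals then arise only if the clause is programmed literally. That is fair as to intent. But with no cross-reference the literal reading cannot be excluded, and two programmers could reach different denominators.

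**The direction depends on event capture.** A reader might infer that the interim rates are certainly too high. The documents do not support that. Including all data available at cut-off is not the same as complete ascertainment to that date. Protocol 10.1.1 has adverse events sought by questioning at each visit, so non-serious events after the last visit may not yet be recorded. If none were recorded, the last-visit denominator would fit the observed events, and in the Step 4 illustration the cut-off denominator would give a rate lower by 175.5 / 4942 = 3.6%. Against this, Protocol 10.1.1 also allows events to be volunteered between visits, and Protocol 10.1.3 requires serious events to be reported within 24 hours of learning of them. Capture in the gap is therefore neither nil nor assured. This point stands and makes the upward bias conditional. It does not remove the mismatch between tables.

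**It is too small to matter for inference.** This is a single-arm study, and the rate has no comparator, test or decision rule. With the assumed 40 events, an exact Poisson 95% interval on the count is roughly 29 to 54, or about −29% to +36%, and a 2–4% shift is well inside that. This also stands, and it sets the priority of the point. Counts, percentages, severity tables and the onset-period table do not use this denominator.

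**Conclusion.** The two sections conflict for continuing participants at the two interim analyses. Followed as written, they give different patient-year totals and an event-rate denominator that ends before the stated event window.

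To the extent that adverse events after the last visit are captured by cut-off, the interim rates would be slightly too high: illustratively about 2–4%, with stress cases of about 13% at Week 28 and 7% at Week 48. The 2–4% rests on 14 continuing participants, an average gap of about two weeks and assumed exposure lengths. It is not a ceiling.

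A reader might also infer that the final safety rates are affected. They are not, because both sections end at the last study visit there. Discontinued participants and the participant who sets the cut-off are likewise unaffected. This is a minor consistency correction that changes no efficacy or safety conclusion.

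**What to change.** In SAP 2.8.1, replace the explanatory clause after the participant-years definition with a reference to the duration of exposure and total patient-years in SAP 2.4.1. At the interim analyses this means the cut-off for continuing participants and the last study visit for discontinued ones; at the final analysis it means the last study visit for all. Use that single total in both the exposure table and the event-rate table.

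The cost is one sentence in the SAP and one shared derived variable in programming. No new data are needed, and no hypothesis test or study procedure changes.

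### The adverse-event table by onset period uses rows of very unequal length with no per-row exposure, so its shape over time partly reflects row width

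*SAP*

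**What the plan says.** SAP 2.8.1 states that "treatment emergent AEs will also be summarized by SOC, PT and onset period at the 28 Week IA and the 48 week IA", and gives support of the registration dossier as the reason. The data for this table are restricted: "using the data up to Week 28 and Week 48, respectively". The interval limits are Days 28, 84, 168, 252 and 336, starting from "0-<4 weeks (1-<28 days" for the first row. The last row is written without an upper limit, from Day 336. For the earlier analysis the SAP adds "Note: at the Week 28 IA, the intervals after 24 weeks will be combined", so the last row there is also written without an upper limit, from Day 168.

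The statistic that 2.8.1 gives for treatment-emergent events is the number and percentage of participants. A rate per 100 participant-years is also planned by system organ class and preferred term. Its denominator runs from first dose to last study visit, and SAP 2.8 fixes its scope for each interim analysis: "Exposure adjusted event rate will be provided for entire treatment period". The onset-period text mentions no person-time, number under observation or rate for a single period, and does not say which denominator a row's percentage uses.

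**The concern.** An onset-period table exists to show when events occur. Its rows can be compared with one another only if they cover similar follow-up, or if each row carries its own follow-up. Here the first three rows double and then triple in length, and the last row is short in both tables because the data stop soon after it opens. Even if the event rate never changed, the percentages would rise and then drop at the end.

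Two misreadings are possible. A low final row may look like better tolerability with longer treatment, although follow-up has simply ended. Conversely, a real excess in the first four weeks may look unremarkable because that row is short. The open-ended labels add to the problem: a reader cannot tell from the label that the last row holds about 30 days in one table and about 2 in the other. The Week 48 analysis is meant to supply long-term safety data, so an almost empty final row is easily over-read there.

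**Working it through.** **Inputs.** Row limits come from SAP 2.8.1. Visit days come from SAP Table 2-1: Week 28 is Day 197 and Week 48 is Day 337; the upper limits of the windows for mapping the end-of-study visit are Days 200 and 340. First dose is Day 1, with no Day 0 (SAP 2.1.1). The number of participants is 14 (SAP 2.5.6 and 2.7.2). The documents give no adverse-event rate, so a constant rate L per participant-year is assumed and varied from 0.2 to 10.

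**The plan's own days.** Visit day = 7 × week + 1 gives 7 × 28 + 1 = 197 and 7 × 48 + 1 = 337, as stated. Row limits equal 7 × week (28, 84, 168, 252, 336), also as stated.

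**Row widths.** Width = last day − first day + 1. The expected percentage of participants with at least one event is 100 × [1 − exp(−L × width / 365.25)], with no dropout.

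| Row (days) | Width | L = 0.2 | L = 1 | L = 4 | L = 10 |
|---|---|---|---|---|---|
| 1–27 (both analyses) | 27 | 1.5% | 7.1% | 25.6% | 52.3% |
| 28–83 (both) | 56 | 3.0% | 14.2% | 45.8% | 78.4% |
| 84–167 (both) | 84 | 4.5% | 20.5% | 60.1% | 90.0% |
| 168–197 (Week 28, last row) | 30 | 1.6% | 7.9% | 28.0% | 56.0% |
| 168–251 (Week 48) | 84 | 4.5% | 20.5% | 60.1% | 90.0% |
| 252–335 (Week 48) | 84 | 4.5% | 20.5% | 60.1% | 90.0% |
| 336–337 (Week 48, last row) | 2 | 0.1% | 0.5% | 2.2% | 5.3% |

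Relative to the first row, the widths are 1 : 2.07 : 3.11 : 1.11 at the Week 28 analysis and 1 : 2.07 : 3.11 : 3.11 : 3.11 : 0.07 at the Week 48 analysis. If the final visit falls on Day 200 or Day 340, the last rows are 33 and 5 days, or 8.6% and 1.4% at L = 1. The pattern does not change.

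**In participants.** At L = 1, the Week 28 drop from 20.5% to 7.9% is 14 × 0.205 = 2.9 against 14 × 0.079 = 1.1 participants.

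**A hidden early excess.** Let the first-row rate be 3 per participant-year and the later rate 1. The first row then shows 1 − exp(−3 × 27 / 365.25) = 19.9%, against 20.5% in the third row. A threefold early excess looks level with it.

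**After adjustment.** Expected events in the first row at L = 1 are 14 × 27 / 365.25 = 1.03, over 1.03 participant-years: 100 per 100 participant-years. The third row gives 3.22 / 3.22, also 100. A constant rate appears constant in every row.

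**The case against.** **The cut-off.** SAP 2.1, 2.8 and 2.14 say that safety analyses at the interim looks use all available data, and open-ended last rows would suit such a table. On that reading the last rows are longer than 30 and 2 days. But 2.8.1 sets a specific limit for this table. Under the general rule, the last row would also have a different length for each participant and would need person-time even more.

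**Visible widths.** The row limits are printed in weeks and days, so a careful reader can allow for the bounded rows. That is fair, but it does not help with the two last rows. In the Week 48 table the three consecutive 84-day rows from Week 12 can be compared directly, apart from dropout.

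**Other outputs.** Overall exposure-adjusted rates are planned, and every event is listed by participant. With 14 participants, timing can be read from the listings. This limits the harm, but one overall rate says nothing about timing.

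**Small numbers.** Most cells by preferred term will hold few participants, and the percentages at L = 1 or above apply mainly to the any-event line. This stands.

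**Stronger readings.** A reader might infer that both tables rise and then collapse after Week 24. Only the Week 28 table does; the Week 48 table rises, stays level and ends in a 2-day remnant. A reader might also infer that the shape is fixed whatever the drug does. It follows exactly only for a constant rate; a strong true trend would change it. Nor do the documents show that the tables will carry no denominators: the SAP leaves them unspecified, and no table shells are available.

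**Conclusion.** The point holds as a matter of presentation that should be corrected before the tables are produced. As specified, the onset-period percentages mix event rate with row width. The longest row is 3.11 times the first. The last row is 30 / 84 = 0.36 of the preceding one at Week 28, and 2 / 84 = 0.02 at Week 48. With a constant rate, that alone produces the rise and fall, at every rate tried from 0.2 to 10 per participant-year.

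The percentages rest on an assumed constant rate, independent events, no dropout, and the Week 28 and Week 48 data limits in SAP 2.8.1. The widths rest only on the SAP's own days. The consequence is confined to a descriptive safety table in about 14 participants. It does not affect the primary analysis, and it should not be read as evidence that the safety conclusions are wrong or that tolerability will be misreported.

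**What to change.** In SAP 2.8.1 and the table shells:

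- For each onset period, show the number of participants under observation at its start and the participant-years accrued in it, and state which denominator the percentages use.
- Give the exposure-adjusted event rate per 100 participant-years for each period, at least for the any-event line and the system-organ-class totals, with the event count beside it.
- Label the last row at the Week 28 analysis as Week 24 to the Week 28 visit.
- At the Week 48 analysis, merge the final row into the preceding one, so that it runs from Day 252 to the Week 48 visit (86 days if that is Day 337). Simply deleting the final row would leave events starting on Days 336–337, or up to Day 340, in no row.
- If the sponsor intends all available data for this table, say so. The participant-years are then still needed.

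The cost is a few lines of SAP text and a modest amount of programming, because participant-years must be split by period. Per-period rates will be imprecise: the first period holds 14 × 27 / 365.25 = 1.03 participant-years, so a single event there is about 97 per 100 participant-years. That is why the counts should stand next to the rates.

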#### **2.8.1.1 Adverse events of special interest / grouping of AEs**

Adverse events of special interest (AESI) (e.g., potential and identified risks) will be defined based on the latest Case Retrieval Strategy (eCRS). Besides the risks defined on the eCRS, the J-RMP potential risk: anaphylactic reaction (SMQ) narrow will also be summarized. The comprehensive search of AESI will be performed for all treatment emergent AEs. Regarding the definition of Canakinumab - immunosuppressants combination therapy toxicity, the newly occurring serious infections which are defined in the eCRS (i.e., “infections – all indications” and “opportunistic infections - IHD indications”) during combination therapy with Canakinumab plus immunosuppressants which are defined in the eCRS (i.e., Anatomical Therapeutic Chemical (ATC) classification drug codes L04AA: selective immunosuppressants, L04AX: other immunosuppressants, L04AB: tumor necrosis factor alpha (TNF-Alpha) inhibitors) will be identified to be summarized.

The number and percentage of participants with AEs of special interest will be summarized.

A listing of the definition of AESI in the eCRS will be provided.

The following safety topics of interest will be identified:

- Neutropenia (all indications)
- Interactions with vaccines (all indications)
- Canakinumab - immunosuppressants combination therapy toxicity (for CAPS PFS and Still's disease)
- Infections (all indications)
- Drug Induced Liver Injury (DILI hepatic transaminase and bilirubin elevations) (Still's disease)
- Opportunistic infections - IHD indications
- Drug reaction with eosinophilia and systemic symptoms (DRESS)
- Malignancy (all indications)
- Macrophage activation syndrome (Still's disease)
- Anaphylactic reaction (SMQ) narrow

The search terms will be based on the latest eCRS (i.e., version 26.0 as of 2-Oct-2023) and the safety topics of interest will be reviewed at each analysis.

